### **7.1.2 Treatment Period**

#### **7.1.2.1 Part 1: Visit 1.1/ Week -5 to -1 ( $\pm 3$ Days)**

Visit 1.1 should be scheduled on the day after dialysis. See [Table 2](#) for a detailed schedule of assessments for this visit.

- Subjects aged between 10 and 12 years will receive a single dose of 500mg lanthanum (as lanthanum carbonate hydrate) and subjects aged 12 years and over will receive a single 1000mg dose lanthanum (as lanthanum carbonate hydrate; SPD405).
- Blood samples for pharmacokinetic analyses will be taken pre-dose and at 3, 5, 6, 8, 12, 24, and 48 hours after dosing.
- Vital signs (blood pressure and pulse) will be recorded pre-dose, and at 24 and 48 hours after dosing.
- A physical examination will be done at 48 hours post-dose.
- Adverse events and changes to concomitant medication will be recorded.

#### **7.1.2.2 Part 2a: Visits 2.1-2.3 (Weeks 2, 4, and 6; $\pm 3$ Days)**

- Subjects will attend the clinic every 2 weeks for scheduled study visits, starting from the first dose of investigational product
- Phosphate and calcium levels will be measured locally for titration purposes.
- The investigational product dispensed at the previous visit will be counted, compliance calculated and the container returned to the subject until exhausted. If necessary, a new container of investigational product will be dispensed.
- The dose of calcium carbonate will be adjusted as required at each visit.
- Any AEs that occurred since the last visit will be recorded.

- A review of any concomitant medication taken since the last visit will be undertaken and changes recorded.
- Confirmation of dialysis adequacy and dietary advice will be made.

#### **7.1.2.3 Part 2a: Visit 2.4 (Week 8; ±3 Days)**

- Vital signs, height, and weight will be measured.
- Blood samples will be taken for biochemistry, and biochemical bone markers.
- Investigational product will be collected and drug accountability performed.
- Any AEs that occurred since the last visit will be recorded.
- A review of any concomitant medication taken since the last visit will be performed and changes recorded.
- Confirmation of dialysis adequacy and dietary advice will be made.
- If phosphate levels remain >6.0mg/dL (1.94mmol/L) for subjects aged under 12 years or >5.5mg/dL (1.78mmol/L) for subjects aged 12 years and older, the subject may be dispensed lanthanum carbonate at a total daily dose of 1500mg to be taken with meals. If phosphate levels are below these levels the subject must enter a washout period of up to 3 weeks or until the targeted levels are reached, whichever is earliest. If a subject has started lanthanum carbonate based on local laboratory results, the subject will be allowed to continue the study even if central laboratory results do not agree.

#### **7.1.2.4 Part 2a: Washout (W2)**

Subjects will be asked to stop taking calcium carbonate and will not be taking a phosphate binder, for up to 3 weeks or until phosphate levels, to be measured locally, of >6.0mg/dL (1.94mmol/L) for subjects aged under 12 years or >5.5mg/dL (1.78mmol/L) for subjects aged 12 years and older are reached, whichever is sooner. The phosphate level should be confirmed by taking a sample (between 0.1-0.7mL depending on each country's specific requirements) which will be analyzed by the central laboratory. If a subject has started lanthanum carbonate based on local laboratory results, the subject will be allowed to continue the study even if central laboratory results do not agree.

Any AEs or changes to concomitant medication will be recorded.

Subjects who complete the 3-week washout (W2) will be dispensed lanthanum carbonate at a starting daily dose of 1500mg to be taken with meals.

Subjects whose phosphate levels do not rise above 6.0mg/dL (1.94mmol/L) for subjects aged under 12 years or >5.5mg/dL (1.78mmol/L) for subjects aged 12 years and older during the washout period may be dispensed lanthanum carbonate for Part 3 at a daily dose determined by the Investigator based on serum phosphorus levels taken at each study visit up to a maximum daily dose of 3000mg which will be taken with meals.

If phosphate levels do not reach the required levels then the subject cannot enter the second treatment period of Part 2, however they can proceed to Part 3.

**7.1.2.5 Part 2a: Visits 2.5-2.7 (Weeks 10, 12, and 14, Nominally;  $\pm 3$  Days)**

- Subjects will attend the clinic every 2 weeks for scheduled study visits.
- At Visit 2.6 only, blood samples will be taken to measure lanthanum pharmacokinetics (2 samples to be selected from: 0-2 hours, 2-4 hours, or 4-6 hours). **Note:** If the sampling is not done at Visit 2.6, blood sampling for pharmacokinetics must be taken at an alternative visit during Part 2.
- Phosphate levels will be measured locally at Visits 2.5, 2.6 and 2.7 only, for titration purposes.
- The investigational product dispensed at the previous visit will be counted, compliance calculated and the container returned to the subject until exhausted. If necessary, a new container of investigational product will be dispensed.
- The dose of lanthanum carbonate will be adjusted and dispensed as required.
- Any AEs that occurred since the last visit will be recorded.
- A review of any concomitant medication taken since the last visit will be undertaken and changes recorded.
- Confirmation of dialysis adequacy and dietary advice will be made.

**7.1.2.6 Part 2a: Final Visit (Visit 2.8; Week 16 Nominally;  $\pm 3$  Days)**

- A 12-lead ECG will be performed.
- Vital signs, height and weight will be measured.
- Blood samples will be taken for biochemistry, and biochemical bone markers.
- Any unused lanthanum carbonate will be collected and drug accountability performed
- Any AEs that occurred since the last visit will be recorded.
- A review of any concomitant medication taken since the last visit will be performed and changes recorded.
- Confirmation of dialysis adequacy and dietary advice will be made.
- For subjects entering Part 3, lanthanum carbonate will be dispensed at a dose determined by the Investigator based on serum phosphorus levels taken at each study visit up to a maximum dose of 3000mg/day.

**7.1.2.7 Part 2b: Visits 2.1-2.3 (Weeks 2, 4, and 6; Nominally;  $\pm 3$  Days)**

- Subjects will attend the clinic every 2 weeks for scheduled study visits, starting from the first dose of investigational product.
- At Visit 2.2 only, blood samples will be taken to measure lanthanum pharmacokinetics (2 samples to be selected from: 0-2 hours, 2-4 hours, or 4-6 hours). **Note:** If the sampling is not done at Visit 2.2, blood sampling for pharmacokinetics must be taken at an alternative visit during Part 2b.

- Phosphate levels will be measured locally at Visits 2.1, 2.2 and 2.3 only, for titration purposes.
- The investigational product dispensed at the previous visit will be counted, compliance calculated and the container returned to the subject until exhausted. If necessary, a new container of investigational product will be dispensed.
- The dose of lanthanum carbonate will be adjusted and dispensed as required.
- Any AEs that occurred since the last visit will be recorded.
- A review of any concomitant medication taken since the last visit will be undertaken and changes recorded.
- Confirmation of dialysis adequacy and dietary advice will be made.

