**Table 1: Schedule of Assessments for Part 1, Part 2a (Treatment Periods 1 and 2), and Part 3**

	Part 1 Subjects who enrol into Part 1 will omit the first washout in Part 2 (Visit window $\pm 3$ days)			Part 2a (Visit window $\pm 3$ days)								Part 3 (Visit window $\pm 1$ week)		
Visit	1.0	Washout W1 j	1.1 a	2.0 b	Washout W1 j	2.1	2.2-2.3	2.4	Washout W2 i	2.5-2.7	2.8	3.0-3.4	3.5/End of Study c	Safety Follow-up call k
Week	-5	-4 to -1	-4 to -1	0	0-3 weeks duration	2 d	4, 6 d	8 d	0-3 week duration	10, 12, 14 d	16 d	20, 24, 28, 32, 36	40 d	41-42 d

b For subjects who have completed Part 1, laboratory and other assessments can be completed from Visit 1.0, no further blood samples are required. A consent form to participate in Part 2a must be signed.

c Assessments scheduled for Visit 3.5 should also be carried out at the time of discontinuation for all subjects who withdraw from the study early or as close as possible to the time of discontinuation. These assessments are not required for subjects post-transplantation, however a safety follow-up call is required.

d Visit weeks may be variable depending on duration of washout (+3 weeks).

e Investigational product will be dispensed at Visit 2.0 if eligible, however if a washout is required then investigational product will be dispensed at visit W1.

f Local laboratory assessments for phosphorus, serum calcium, and calcium phosphorus product in Parts 1 and 2 are for titration purposes, as required, and will not be analyzed; data from Visits 3.0-3.4 will be collected and assessed.

g Visit 2.6 only; Each subject will have at least 2 samples taken for pharmacokinetic assessment. These should be taken during defined time windows (to be selected from: 0-2 hours, 2-4 hours and 4-6 hours, after the first dose/meal of the day). Note: If the sampling is not done at Visit 2.6, blood sampling for pharmacokinetics must be taken at an alternative visit during Part 2.

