**Table 3: Schedule of Assessments for Part 2b and Part 3**

	Part 2b (Visit window ±3 days)				Part 3 (Visit window ±1 week)		
Visit	1.0a	Washout W1b	2.1-2.3	2.4	3.0-3.4	3.5/End of Studyc	Safety Follow-up callj
Week	0	0-3 weeks duration	2, 4, 6d	8d	12, 16, 20, 24, 28	32d	33-34d

d Visit weeks may be variable depending on duration of washout (+3 weeks).

e Local laboratory assessments for phosphorus in Part 2b are for titration purposes, as required, and will not be analyzed; data from Visits 3.0-3.4 will be collected and assessed.

f Visit 2.2 only; Each subject will have at least 2 samples taken for pharmacokinetic assessment. These should be taken during defined time windows (to be selected from: 0-2 hours, 2-4 hours and 4-6 hours, after the first dose/meal of the day). Note: If the sampling is not done at Visit 2.2, blood sampling for pharmacokinetics must be taken at an alternative visit during Part 2b.

g Visit 3.3 only; Each subject will have at least 2 samples taken for pharmacokinetic assessment. These should be taken during defined time windows (to be selected from: 0-2 hours, 2-4 hours and 4-6 hours, after the first dose/meal of the day). Note: If the sampling is not done at Visit 3.3, blood sampling for pharmacokinetics must be taken at an alternative visit during Part 3.

h Investigational product will be dispensed at Visit 1.0 if eligible, however if a washout is required then investigational product will be dispensed at visit W1.

i For subjects entering Part 3 only.

j Safety follow-up call to be made 7-14 days following last dose of investigational product. For subjects discontinued due to kidney transplantation, the safety follow up call to be made 30 ± 7 days from the last dose.

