### **Hypocalcemia During Parts 2 and 3**

Subjects whose serum levels of corrected total calcium are below the lower limit (<8.8mg/dL [2.20mmol/L]) should receive therapy to increase serum calcium levels. This must be taken between meals and/or at bedtime.

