### **Hypercalcemia**

If hypercalcaemia (serum calcium >10.2mg/dL (2.54mmol/L) develops during administration of calcium carbonate in Part 2a (Treatment Period 1) of the study, active vitamin D sterols should be decreased by 50%, the dose of calcium carbonate should be decreased by 25%, and the subject should be monitored. If after 2 weeks hypercalcemia persists, active vitamin D sterols should be stopped. If after another 2 weeks from onset of hypercalcemia it persists, the subject should be withdrawn from Part 2a. If the Investigator believes there are no contraindications and the subject is willing to continue, the subject can start Part 3.

If hypercalcemia (serum calcium >10.2mg/dL (2.54mmol/L) develops during administration of lanthanum carbonate, active vitamin D sterols should be decreased by 50%. If after 2 weeks hypercalcemia persists, active vitamin D sterols should be stopped until required.

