**7.1.2.8 Part 2b: Final Visit (Visit 2.4; Week 8; Nominally;  $\pm 3$  Days)**

- A 12-lead ECG will be performed.
- Vital signs, height and weight will be measured.
- Blood samples will be taken for biochemistry, and biochemical bone markers.
- Any unused lanthanum carbonate will be collected and drug accountability performed.
- Any AEs that occurred since the last visit will be recorded.
- A review of any concomitant medication taken since the last visit will be performed and changes recorded.
- Confirmation of dialysis adequacy and dietary advice will be made.
- For subjects entering Part 3, lanthanum carbonate will be dispensed at a dose determined by the Investigator based on serum phosphorus levels taken at each study visit up to a maximum dose of 3000mg/day.

**7.1.2.9 Part 3 (Visits 3.0-3.4: Weeks 20, 24, 28, 32, and 36;  $\pm 1$  Week for Part 2a; Weeks 12, 16, 20, 24, and 28 for Part 2b)**

- Subjects who have successfully completed Part 2 of the study will continue to be dispensed lanthanum carbonate for a further 6 months.
- Subjects will attend the clinic once every month for scheduled study visits.
- At Visits 3.0-3.4 the local lab results for serum calcium, serum phosphorus, and calcium phosphorus product will be taken for analysis.
- At Visit 3.3 only, blood samples will be taken to measure lanthanum pharmacokinetics (2 samples to be selected from: pre dose to 2 hours, 2-4 hours, and 4-6 hours). **Note:** If the sampling is not done at Visit 3.3, blood sampling for pharmacokinetics must be taken at an alternative visit during Part 3.
- The dose of lanthanum carbonate will be adjusted and dispensed as required and any unused lanthanum carbonate will be collected, and drug accountability performed.
- Any AEs that occurred since the last visit will be recorded.

- A review of any concomitant medication taken since the last visit will be undertaken and changes recorded.
- Confirmation of dialysis adequacy and dietary advice will be made.

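### Part 2b schedules no calcium measurement between Visit 1.0 and Week 8, although the protocol's low- and high-calcium rules apply during that lanthanum treatment

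*Protocol*

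**What the plan says.** **The calcium rules.** Protocol Section 6.2.1 has a low-calcium rule covering Parts 2 and 3, for "Subjects whose serum levels of corrected total calcium are below the lower limit" of 8.8 mg/dL. It also has a high-calcium rule during lanthanum treatment, starting above 10.2 mg/dL, with a second step: "If after 2 weeks hypercalcemia persists, active vitamin D sterols should be stopped until required". Appendix 2 lists both thresholds and repeats the 2-week step. Section 5.2 ties changes in vitamin D dose to the same high-calcium rule.

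**Part 2b (lanthanum only).** For Weeks 2, 4 and 6, Section 7.1.2.7 says "Phosphate levels will be measured locally at Visits 2.1, 2.2 and 2.3 only, for titration purposes". Table 3 footnote e reads "Local laboratory assessments for phosphorus in Part 2b are for titration purposes, as required, and will not be analyzed". At Week 8, Section 7.1.2.8 says "Blood samples will be taken for biochemistry, and biochemical bone markers"; Section 7.2.3.5 puts calcium in that biochemistry panel.

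**Part 2a Treatment Period 2 (lanthanum).** Section 7.1.2.5 says "Phosphate levels will be measured locally at Visits 2.5, 2.6 and 2.7 only, for titration purposes". Table 1 ticks local laboratory tests at these visits, and its footnote f reads "Local laboratory assessments for phosphorus, serum calcium, and calcium phosphorus product in Parts 1 and 2 are for titration purposes, as required".

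**Where calcium is named.** For the calcium carbonate period, Section 7.1.2.2 says "Phosphate and calcium levels will be measured locally for titration purposes". For Part 3, Section 7.1.2.9 names local serum calcium at every visit from 3.0 to 3.4.

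**The concern.** A rule that acts on a laboratory value needs that value at the time the rule refers to. In Part 2b the visit text and the schedule table both leave calcium out of the three interim visits. A site that follows them exactly has nothing scheduled with which to start the low- or high-calcium action before Week 8, or to judge persistence 2 weeks later. Application of the rules then depends on calcium tests that the protocol does not prompt, and practice may differ across up to 36 sites.

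The setting makes this more than a missing detail. All new subjects enter Part 2b. The redesign moved the focus of the study to safety (Section 3.1). The exclusion criteria in Section 4.2 set no calcium limit, so a child may start lanthanum with calcium already outside 8.8 to 10.2 mg/dL. There is no Data Monitoring Committee (Section 9.4).

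There is a smaller reporting consequence. Section 8.1.5 allows a laboratory change to be recorded as an adverse event, and SAP Section 11.1 tabulates Part 2 treatment-emergent events by treatment group. If calcium is checked more often in one period than in another, investigators have unequal opportunity to record calcium events.

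**Working it through.** The plan states no figure to reproduce. The check is a count of scheduled calcium results from the schedule tables, their footnotes, the visit text and the biochemistry panel in Section 7.2.3.5.

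| Period | Analytes named in visit text, interim visits | Local tests in schedule table | Scheduled biochemistry (includes calcium) | Interim calcium results |
|---|---|---|---|---|
| Part 2a, Period 1 (calcium carbonate) | Phosphate and calcium, Weeks 2, 4, 6 (7.1.2.2) | Ticked; footnote f includes calcium | Visits 2.0, 2.4 | 3 |
| Part 2a, Period 2 (lanthanum) | Phosphate, Visits 2.5-2.7 (7.1.2.5) | Ticked; footnote f includes calcium where needed | Visits 2.4, 2.8 | 0 by visit text; up to 3 by footnote f |
| Part 2b (lanthanum) | Phosphate, Visits 2.1-2.3 (7.1.2.7) | Ticked; footnote e names phosphorus | Visits 1.0, 2.4 | 0 |
| Part 3 (lanthanum) | Calcium, phosphorus and their product, Visits 3.0-3.4 (7.1.2.9) | Ticked | Visit 3.5 | 5 |

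The central sample at the Part 2b washout visit (W1) is described only as a phosphate confirmation, so it adds no calcium value.

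**Length of the Part 2b gap.**
- Without washout: Week 8 - Week 0 = 8 weeks.
- With the full washout: 3 + 8 = 11 weeks from the Visit 1.0 sample, of which 8 are on lanthanum.

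**The 2-week step.**
- Within Part 2b, the rule needs a first high value and another about 2 weeks later. Scheduled calcium values at Weeks 2, 4 and 6: none. Neither step has a scheduled value before Week 8.
- If the first high value is the Week 8 result, the second would be due at Week 8 + 2 = Week 10. The next visit is 3.0, at Week 12, for subjects who enter Part 3.
- The visit windows do not close this. With Visit 2.4 at its latest (day 56 + 3 = 59) and Visit 3.0 at its earliest (day 84 - 7 = 77), the interval is 77 - 59 = 18 days, still longer than 14.

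**Opportunity to record a calcium event in Part 2.** Scheduled on-treatment calcium results, interim plus end of period:
- Calcium carbonate: 3 + 1 = 4.
- Part 2b lanthanum: 0 + 1 = 1.
- Part 2a lanthanum: between 0 + 1 = 1 and 3 + 1 = 4, depending on whether the visit text or footnote f is followed.

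The effect on event counts cannot be sized, because the documents give no rate of calcium excursions.

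**The case against.** **Silence is not prohibition.** In the Section 7.1.2.7 sentence, the word only limits the visits and not the analyte. The Table 3 row is headed local laboratory tests, without naming phosphate. Footnote e is not a full list of analytes either: it also covers Visits 3.0-3.4 without naming calcium, although Section 7.1.2.9 takes calcium there. SAP Section 10.3 allows local data to replace missing central calcium in Part 2 without separating Part 2a from Part 2b. Section 7.2.3.5 lets unexpected abnormal values be repeated. This stands. A reader might infer that sites cannot detect an excursion or cannot apply the rules; the documents do not support that. What remains is that no calcium value is scheduled.

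**Part 2a.** A reader might extend the gap to all lanthanum treatment in Part 2. Table 1 and footnote f prevent that. For Treatment Period 2 there is a disagreement between visit text and table, and absence of testing is not shown.

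**The difference may be deliberate.** Calcium carbonate carries calcium-based stopping and withdrawal rules (Sections 4.4.1 and 6.2.1) and lanthanum does not, so closer calcium checks under a calcium-containing binder are defensible. That could explain a lower frequency. It does not explain a 2-week step with no scheduled value, and no passage gives this reason.

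**Comparison.** A reader might infer that the safety objective compares calcium events between treatments. It does not: the first secondary objective is descriptive. The central biochemistry summaries by visit (SAP Section 11.2) are also largely symmetric, with a sample at the end of each 8-week period. Only investigator-reported adverse events, shown by treatment group, are open to unequal detection.

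**The 11 weeks.** Up to 3 of these fall before lanthanum starts. The on-lanthanum interval is 8 weeks.

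**Conclusion.** The point holds in full for Part 2b. Visit text and schedule table agree, and neither places a calcium measurement between Visit 1.0 and Visit 2.4. The first scheduled on-lanthanum value is at Week 8, up to about 11 weeks after the screening sample, while the protocol's low- and high-calcium rules already apply and one of them has a 2-week step. After Week 8 the next scheduled visit is 4 weeks later.

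For Part 2a Treatment Period 2 the finding is an inconsistency: there are no interim calcium results by Section 7.1.2.5 and up to three by Table 1 footnote f.

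Unequal detection of investigator-reported calcium events in the Part 2 tables is possible, with fewer scheduled opportunities in Part 2b than under calcium carbonate (1 against 4). Its size is unknown.

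These conclusions rest on reading the schedule as written and counting scheduled tests only. Sites that measure calcium in routine care would have more values than counted here.

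**What to change.** Reconcile Sections 7.1.2.5 and 7.1.2.7, Table 1 footnote f and Table 3 footnote e with Section 6.2.1 and Appendix 2, so that the schedule of calcium results matches the times at which the protocol's own calcium rules need them. Carry the result into the schedule tables and footnotes reproduced in the SAP. The choice of analytes, and the calcium thresholds and actions, are for the sponsor; nothing here asks for them to change.

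The cost is an amendment to two visit paragraphs and two footnotes. A local sample is already taken at Visits 2.1-2.3 in Part 2b and 2.5-2.7 in Part 2a, so no extra visit is needed. Table 5 gives no volume for local samples, so any added blood volume should be checked against the local limits in exclusion criterion 7.

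If Part 2 adverse events are tabulated by treatment group under the present schedule, a note to the tables should state how often calcium was scheduled in each period.

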**7.1.2.8 Part 2b: Final Visit (Visit 2.4; Week 8; Nominally;  $\pm 3$  Days)**

- A 12-lead ECG will be performed.
- Vital signs, height and weight will be measured.
- Blood samples will be taken for biochemistry, and biochemical bone markers.
- Any unused lanthanum carbonate will be collected and drug accountability performed.
- Any AEs that occurred since the last visit will be recorded.
- A review of any concomitant medication taken since the last visit will be performed and changes recorded.
- Confirmation of dialysis adequacy and dietary advice will be made.
- For subjects entering Part 3, lanthanum carbonate will be dispensed at a dose determined by the Investigator based on serum phosphorus levels taken at each study visit up to a maximum dose of 3000mg/day.

**7.1.2.9 Part 3 (Visits 3.0-3.4: Weeks 20, 24, 28, 32, and 36;  $\pm 1$  Week for Part 2a; Weeks 12, 16, 20, 24, and 28 for Part 2b)**

- Subjects who have successfully completed Part 2 of the study will continue to be dispensed lanthanum carbonate for a further 6 months.
- Subjects will attend the clinic once every month for scheduled study visits.
- At Visits 3.0-3.4 the local lab results for serum calcium, serum phosphorus, and calcium phosphorus product will be taken for analysis.
- At Visit 3.3 only, blood samples will be taken to measure lanthanum pharmacokinetics (2 samples to be selected from: pre dose to 2 hours, 2-4 hours, and 4-6 hours). **Note:** If the sampling is not done at Visit 3.3, blood sampling for pharmacokinetics must be taken at an alternative visit during Part 3.
- The dose of lanthanum carbonate will be adjusted and dispensed as required and any unused lanthanum carbonate will be collected, and drug accountability performed.
- Any AEs that occurred since the last visit will be recorded.

- A review of any concomitant medication taken since the last visit will be undertaken and changes recorded.
- Confirmation of dialysis adequacy and dietary advice will be made.

